9.4.3 ANALYSIS OF THE SECONDARY ENDPOINT(S)

We also hypothesize that iCO will reduce the severity of ARDS as measured by lung injury score (LIS), $\text{PaO}_2/\text{FiO}_2$, oxygenation index (OI), and dead space fraction (Vd/Vt). These endpoints will be analyzed using repeated measures analysis of covariance (ANCOVA) to assess the effects of treatment, time, and the interaction between time and treatment, while incorporating between-patient variation in baseline measurements and important covariates including smoking, age, sex, and severity of ARDS. Age and sex will be considered as important biological variables in all analyses.

Interaction contrasts will include polynomial trends across time, focusing on a linear trend suggesting improvement and a quadratic trend suggesting that improvement is leveling off. As part of our analysis, we will also include the interaction between treatment and entry criteria (ARDS/Sepsis vs. Non-ARDS/Sepsis Pneumonia vs. Non-ARDS/non-Sepsis Pneumonia) in the model. Because the study is not powered for the interaction between treatment and entry criteria, that test will be exploratory. We will also perform post-hoc analyses within each criteria group to generate hypotheses for future study.

With 24 subjects in the CO group and 12 subjects in the placebo arm, we will have 80% power ($\alpha=0.05$) to detect a 0.95 difference in LIS between treatment arms, assuming a conservative SD of 0.8 (**Table 7**). We will also have 80% power to detect a 78.6 mm Hg difference in $\text{PaO}_2/\text{FiO}_2$, a 12.0 difference in OI, and a 0.14 difference in Vd/Vt between treatment arms, assuming SDs of 66, 10.1, and 0.12 respectively.

Table 7. Minimal detectable difference at 80% power.

| Endpoint | SD | Detectable Difference ($\alpha= 0.05$) |
|-----------------------------|-----|--|
| LIS | 0.8 | 0.95 |
| $\text{PaO}_2/\text{FiO}_2$ | 66 | 78.6 |

| Endpoint | SD | Detectable Difference ($\alpha= 0.05$) |
|----------|------|---|
| OI | 10.1 | 12.0 |
| Vd/Vt | 0.12 | 0.14 |

Ventilator-free days (VFDs), hospital- and ICU-free days, and Sequential Organ Failure Assessment (SOFA) scores will each be analyzed separately using ANCOVA with treatment arm as the main effect. Given our modest sample size, we will only be powered to see large changes.

Results from the Hayling Sentence Completion Test and Montreal Cognitive Assessment (MoCA) testing will be compared between CO and placebo groups using the Mann-Whitney U test or t-test (if normally distributed). If significantly different between the groups, scores from the Hayling Sentence Completion Test and MoCA testing may be incorporated into exploratory multiple regression analyses.

Mortality will be analyzed using Cox regression models for time-to-death with treatment arm as the main predictor, and with important covariates including smoking, age, and sex in the model. Hazard ratio (HR) and 95% CI for CO relative to placebo will be reported, along with Kaplan-Meier plots and estimated proportions surviving at 28, 60, and 180 days.

To address potential bias from unobserved study outcomes due to missed visits, premature withdrawal, or death and to ensure robust data analyses, we will work closely with [name] at Johns Hopkins University, who has extensive expertise with long-term outcomes assessment after acute respiratory failure and critical illness. [name] will provide his expertise and assist with statistical methods developed by his Outcomes After Critical Illness and Surgery (OACIS) Group to address missing data and assess long-term outcomes that may be “truncated due to death”. We will use the statistical software application developed by his group using R and Shiny to impute missing data among survivors given the high mortality in ARDS. We will also employ other statistical approaches used by his OACIS Group to assess long-term outcomes in critically ill patients. These include a composite endpoint approach using both functional outcome and survival, as well as other statistical methods (e.g. survivors only analyses and survivor average causal effect [SACE]).

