6.3 MEASURES TO MINIMIZE BIAS: RANDOMIZATION AND BLINDING

Eligible participants will be randomized to one of the two treatment arms using a permuted block method¹⁴⁶ with random block sizes. The randomization ratio will be 2:1 iCO:placebo. The randomization will not be stratified by any factors. The study biostatistician will verify all the necessary randomization information (blinding method, randomization method, block size, and number of treatment groups) in the StudyTRAX randomization configuration module.

Site investigators will review all potential study participants with one of the CCC physician members. Following informed consent, the unblinded administering RT or physician or blinded study coordinator will randomize subjects in the database using the StudyTRAX randomization tool. The unblinded administering RT or physician will obtain the subject's treatment assignment through the "View Treatment" button in the blinded database, a privilege granted to unblinded RTs and physicians only. CO-related measurements (SpCO, COHb, ambient CO) and drug-related information will be in a separate project within the database, which the blinded study coordinators will not have access to. Permission to this limited-access project will only be granted to unblinded study personnel by the PI, as it contains treatment-specific information such as CO monitoring and study drug administration data.

The study drug assignment will be blinded to the subject, clinical team, study coordinators, and other study staff with the exception of the administering study staff (RT and physician OR physician alone), who will be unblinded to the treatment assignment to ensure subject safety. We chose this partially double-blind design to ensure safe iCO administration and an unblinded assessment of COHb levels in order not to exceed potentially toxic thresholds.

To maintain blinding, the placebo air cylinders are identical in appearance as the CO cylinders (with the exception of different CGA valves required by the manufacturer Praxair). Cylinders will also be shrouded in dark sleeves to ensure blinding. The placebo air will be administered via inhalation via the COventDS

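### Section 9.4.3 puts the treatment-by-entry-criteria interaction into the ANCOVA that supplies the treatment effect without defining that effect, so the stated 80% power may be lost if the pneumonia groups are small

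*Combined protocol and SAP*

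**What the plan says.** Section 9.4.3 assigns LIS, PaO2/FiO2, OI and Vd/Vt to a repeated measures ANCOVA with treatment, time, treatment by time, baseline and covariates. The next paragraph states: "As part of our analysis, we will also include the interaction between treatment and entry criteria". The sentence lists three entry groups (ARDS with sepsis, pneumonia with sepsis but no ARDS, pneumonia with neither) and places the term in the model. The section then says the study is not powered for this interaction and calls that test exploratory. It says nothing about coding, type of sums of squares or weights for the treatment effect.

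The power statement that follows is for a plain difference between arms: "we will have 80% power ($\alpha=0.05$) to detect a 0.95 difference in LIS between treatment arms, assuming a conservative SD of 0.8". It opens with the arm sizes: "With 24 subjects in the CO group and 12 subjects in the placebo arm". Table 7 covers the other three endpoints in the same way.

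Section 6.3 says of allocation: "The randomization will not be stratified by any factors". Section 2.1 dates the addition of pneumonia patients to April 2023. No expected or minimum size is given for any entry group.

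**The concern.** Once a treatment-by-group interaction is in a model, the treatment main effect has no fixed meaning until the coding or weighting is stated. Two common defaults give something other than the overall iCO-placebo difference. One gives each entry group one-third weight however few patients it holds; the other reports the effect in a single group.

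The pneumonia groups may be small. They were added by amendment, and the last sentence of the pneumonia criteria in section 5.1, read literally, sends some pneumonia patients back to the ARDS and sepsis group. With 36 subjects and no stratification, a small group can also end up with nobody in one arm. At stake are the precision and meaning of the treatment estimate for four endpoints with explicit power claims, and the freedom to choose a coding after the data are seen.

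**Working it through.** **Inputs.** From section 9.4.3: 24 CO and 12 placebo; alpha 0.05 (taken as two-sided, since the plan does not say); LIS difference 0.95 with SD 0.8; PaO2/FiO2 78.6 with SD 66; OI 12.0 with SD 10.1; Vd/Vt 0.14 with SD 0.12; three entry groups. Assumed: the entry-group sizes, each split 2:1. Gains from repeated measures and covariates are ignored.

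**Step 1: the plan's own figure.** Standardized differences are 0.95/0.8 = 1.19, 78.6/66 = 1.19, 12.0/10.1 = 1.19 and 0.14/0.12 = 1.17. The variance of a 24 versus 12 difference, in SD² units, is 1/24 + 1/12 = 0.125. Noncentral-t power on 34 df is 90% for LIS, 91% for PaO2/FiO2, 90% for OI and 89% for Vd/Vt. The stated 80% is not reproduced. The difference detectable with 80% power is 1.02 SD (LIS 0.82), so Table 7 is conservative by about 10 points for the plain comparison.

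**Step 2: variance of each candidate treatment effect.** A group of n subjects split 2:1 has variance 1/(2n/3) + 1/(n/3) = 4.5/n.

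- Equal-weight mean: (1/9) × Σ(4.5/n_k) = 0.5 × Σ(1/n_k).
- Reference-group effect: 4.5/n_ref.
- Weighted by observed size: Σ(n_k/36)² × 4.5/n_k = 4.5 × 36/36² = 0.125, whatever the mix.

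For example, 24/6/6 gives 0.5 × (1/24 + 1/6 + 1/6) = 0.1875. The SE ratio to the plain comparison is √(0.1875/0.125) = 1.22.

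**Step 3: chance of an empty cell.** Treat the 12 placebo subjects as a random draw from 36. The chance is 1 − ΣC(n₁,p₁)C(n₂,p₂)C(n₃,p₃)/C(36,12), summed over placebo counts p_k that leave both arms present in every group. For a single group of 3, the chance that one arm is missing is [C(24,3) + C(12,3)]/C(36,3) = 0.283 + 0.031 = 0.314.

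**Step 4: results.** Power is at the LIS difference (1.19 SD) on 36 − 6 = 30 df. Group order is ARDS/sepsis, then the two pneumonia groups.

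| Assumed sizes | Equal-weight variance | Equal-weight power | Power, largest group as reference | Chance of an empty cell |
|---|---|---|---|---|
| 12/12/12 | 0.125 | 90% | 47% | about 1% |
| 18/9/9 | 0.139 | 87% | 63% | 3% |
| 21/9/6 | 0.163 | 81% | 70% | 8% |
| 24/6/6 | 0.188 | 76% | 76% | 14% |
| 28/4/4 | 0.268 | 60% | 82% | 35% |
| 30/3/3 | 0.350 | 49% | 84% | 54% |

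The 28/4/4 row uses fractional 2:1 splits. With a reference group of 27 the variance is 4.5/27 = 0.167 and power is 80%, so reference coding falls short of 80% unless that group holds about 27 or more of the 36. If arm counts within groups vary by chance, equal-weight power when estimable falls to 87%, 83%, 77%, 71% and 49% for 12/12/12, 18/9/9, 21/9/6, 24/6/6 and 30/3/3. The size-weighted effect has about 90% power for every mix with 2:1 splits.

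**Step 5: wording compared.** For 90-minute COHb, sections 9.4.2 and 9.4.5 run the ANOVA on treatment and time first and then repeat it with entry criteria and interactions. Section 9.4.3 has no such two-step wording.

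**The case against.** The strongest reply is that the plan does not commit to an equal-weight or single-group effect. Type II or sequential tests, or observed-margin weights, keep an overall effect with the interaction present. Section 9.4.3 also describes the ANCOVA without entry criteria first, and section 9.4.1 provides a general t-test or Mann-Whitney comparison between arms. The COHb analysis shows that the authors know the two-step approach, and a two-step reading of 9.4.3 is possible. Much of this stands: the defect is an unspecified contrast, not a planned wrong one. It does not close the gap, because 9.4.3 assigns ANCOVA specifically to these endpoints and does not say which fit or contrast gives the treatment effect.

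A reader might infer that the planned model necessarily lacks the stated power or leaves the overall effect undefined. The documents do not support that. Table 7's differences have about 90% power in the plain comparison, so balanced or moderately uneven groups still reach 80% under equal weighting when splits are 2:1. Lower figures, such as 63% for 24/6/6 and 39% for 30/3/3, apply at 1.02 SD, which is not a difference the plan states. An empty cell also leaves a reference-group effect estimable when the reference group has both arms.

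Nor do the documents show that the pneumonia groups will be small. They give no enrolment by entry group, and section 5.4 cites the need to expand enrolment, which fits sizeable groups as well as small ones.

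**Conclusion.** The point holds conditionally. Section 9.4.3 leaves the treatment effect for four secondary endpoints undefined once the interaction is in the model, and two common defaults do not give the contrast that Table 7 powers. Under equal weighting with 2:1 splits, the stated 80% is kept up to about 21/9/6 and lost in the more uneven mixes examined. Under reference coding with the largest group as reference, it is lost unless that group has about 27 or more subjects. Non-estimability of the equal-weight effect is a serious risk only when a pneumonia group is small.

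All of this rests on assumed group sizes and an unstated coding. The endpoints are secondary in a 36-subject Phase Ib trial whose sample size rests on COHb accuracy (section 9.2). Severity is minor to moderate; the change is a free improvement.

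**What to change.** In section 9.4.3, state that the treatment effect and its confidence interval for LIS, PaO2/FiO2, OI and Vd/Vt come from the repeated measures ANCOVA with entry criteria as a main effect only. Then state that the model will be repeated with treatment by entry criteria as a separate exploratory analysis, as section 9.4.2 does for COHb, and that no overall treatment effect will be read from that second model.

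The cost is one or two sentences in the analysis plan. No new data, subjects or procedures are needed. With 2:1 splits, power at Table 7's LIS difference is then about 90% whatever the mix of entry groups, and an empty cell no longer prevents estimation of the overall effect.

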9.2 SAMPLE SIZE DETERMINATION

As the primary endpoint of this Phase Ib trial is safety, this sample size of 36 (2:1 CO:placebo) was chosen based on a probability to estimate the mean difference between measured and predicted COHb levels in the CO group within 0.5% with 95% confidence to support the accuracy of the CFK equation.

Our preliminary data from our Phase Ia trial demonstrate that the CFK equation is highly accurate at predicting COHb levels following a 20 minute exposure to 200 ppm iCO ($r=0.916$, $R^2=0.9204$; $p<0.0001$). The mean difference between measured and predicted COHb levels was 0.1467 ± 0.2738 . Using a more conservative estimate of standard deviation (SD)=0.6, we will have >99% probability that 95% confidence intervals around the mean difference between measured and predicted COHb levels will be -0.353% to 0.647%. Our calculation includes an 8% dropout rate.

The goal of the safety evaluation for this study is to identify safety concerns associated with CO administration. The ability of the study to detect administration-related AEs or SAEs can be expressed by the true event rate above which at least one SAE would likely be observed and the true event rate below which no events would likely be observed. Specifically, for the CO arm of the study (n=24), there is a 90% probability of observing at least one AE if the true background rate of that AE is 10% and a 97% probability of observing at least one AE if the true background rate of that AE is 15%. For the placebo arm of the study (n=12), there is an 83% probability of observing at least one AE if the true background rate of that AE is 15% and a 91% probability of observing at least one AE if the true background rate of that AE is 20%. In our Phase Ia trial, there were no administration-related AEs and no SAEs related to study product or procedures.

Probabilities of observing one or more events between the groups are presented in **Table 6** below for a range of possible true AE rates. These calculations provide a more complete picture of the sensitivity of this study design to identify potential safety problems with CO.

Table 6. Probability of observing 1 or more events between the groups for different true AE rates

| CO group | | | Placebo Group | | |
|----------|--------------|-----------------------------|---------------|--------------|-----------------------------|
| n | True AE rate | Power to detect ≥ 1 AE | N | True AE rate | Power to detect ≥ 1 AE |

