9.3 POPULATIONS FOR ANALYSES

All randomized participants will be included in the intent-to-treat (ITT) population. All randomized subjects who receive at least one dose of study product (CO vs. placebo) will be included in the safety analyses (*i.e.*.. modified ITT). For secondary and exploratory endpoints, subjects may also be analyzed according to the number of study drug doses completed.

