9.4.4 ANALYSIS OF EXPLORATORY ENDPOINTS (BIOMARKERS)

We will compare biological outcomes between treatment arms using the Mann-Whitney U or t-test for numerical endpoints and either χ^2 or Fisher’s exact test for categorical outcomes. Lipid mediators (LM) and specialized pro-resolving mediators (SPM) levels will be analyzed using principal component analysis (PCA).

We hypothesize that treatment with iCO will reduce plasma levels of mitochondrial DNA (mtDNA), IL-18, and receptor-interacting serine/threonine-protein kinase 3 (RIPK3). Circulating IL-18, mtDNA, and RIPK3 levels will be log transformed before analysis. Based on our prior work, the SD of the log-IL-18 is approximately 0.7, approximately 1.0 for mtDNA, and approximately 2.0 for RIPK3. With 12 subjects in the placebo arm and 24 in the iCO arm, we will have 80% power to detect a difference in IL-18 levels of 0.834 log, which corresponds to an approximate 2-fold difference in plasma IL-18. We will have 80% power to detect a difference in mtDNA of 1.190 log, which corresponds to an approximate 3-fold difference in the circulating mtDNA copy number between the iCO and placebo groups.

We will also have 80% power to detect a difference in RIPK3 of 2.38 log, which corresponds to an approximate 8-10-fold difference in the circulating RIPK3 levels between the iCO and placebo groups. While the magnitude of the putative CO effect on these 3 biomarkers is unknown, we found a 3-fold difference in IL-18 between sepsis patients with and without ARDS and a 4-fold difference in mtDNA between sepsis/ARDS patients and controls. Similarly, we found a 7-fold difference in median RIP3K levels between patients with organ failure and shock compared with ICU patients without organ failure or shock. Therefore detecting differences of these magnitudes is feasible in this patient population. Based on our preliminary data, we will also have 80% power ($\alpha=0.05$) to detect a difference in a number of LM and SPM including PGD₂, PGE₂, PGF_{2 α} , TXB₂, RvD2, and Mar1 (**Table 8**).

Table 8. Minimal detectable difference at 80% power.

| | Mediator | Standard Deviation | Detectable Difference (pg/mL) |
|----------------------------|-------------------------------------|---------------------------|--------------------------------------|
| Pro-inflammatory LM | LTB ₄ | 17.95 | 21.4 |
| | PGD ₂ | 0.68 | 0.81 |
| | PGE ₂ | 1.68 | 2.00 |
| | PGF _{2α} | 1.15 | 1.37 |
| | TXB ₂ | 12.38 | 14.75 |

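### The 80%-power detectable differences in Tables 7 and 8 and the biomarker text (about 1.19 SD) do not follow from the stated 24 vs 12 subjects (1.02 SD) or from the stated 8% dropout (1.07 SD)

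*Combined protocol and SAP*

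**What the plan says.** Section 9.4.3, before Table 7: "With 24 subjects in the CO group and 12 subjects in the placebo arm, we will have 80% power" at alpha 0.05. The differences listed are LIS 0.95, PaO2/FiO2 78.6, OI 12.0 and Vd/Vt 0.14, with SDs of 0.8, 66, 10.1 and 0.12.

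Section 9.4.4, log biomarkers: "With 12 subjects in the placebo arm and 24 in the iCO arm, we will have 80% power" for IL-18 0.834, mtDNA 1.190 and RIPK3 2.38 log, with SDs of 0.7, 1.0 and 2.0. For RIPK3 it claims "80% power to detect a difference in RIPK3 of 2.38 log, which corresponds to an approximate 8-10-fold difference". It then cites earlier observations, among them "we found a 7-fold difference in median RIP3K levels", and concludes: "Therefore detecting differences of these magnitudes is feasible in this patient population". Table 8 adds eight lipid mediators at the same power and alpha.

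The only attrition figure is in section 9.2, with the COHb precision calculation: "Our calculation includes an 8% dropout rate". The same section says of Table 6 that "for the CO arm of the study (n=24), there is a 90% probability of observing at least one AE" when the true rate is 10%. Section 9.3 defines the safety set: "All randomized subjects who receive at least one dose of study product (CO vs. placebo) will be included in the safety analyses". Section 1.4 sets the enrolment goal at 36 subjects who are both randomized and treated.

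**The concern.** A detectable difference divided by its SD depends only on the two group sizes, alpha and power. Here that ratio is the same for endpoints on quite different scales, so one multiplier was used throughout, and it is not the one the stated inputs give. A reader cannot reproduce the figures. Anyone who takes them as what 24 vs 12 can detect will understate the trial's sensitivity, including when planning a later study. The RIPK3 passage has a further problem: its feasibility conclusion rests on a benchmark smaller than the difference the same paragraph says is detectable.

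**Working it through.** **Inputs.** Group sizes 24 and 12 (sections 9.4.3, 9.4.4); power 80% and alpha 0.05 (same sections; sidedness is not stated, two-sided assumed); dropout 8% (section 9.2), giving 24 × 0.92 = 22.1 and 12 × 0.92 = 11.0, so 22 vs 11. SDs and differences are as printed.

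**Printed ratios (difference / SD).** LIS 0.95/0.8 = 1.188; PaO2/FiO2 78.6/66 = 1.191; OI 12.0/10.1 = 1.188; Vd/Vt 0.14/0.12 = 1.167 (1.19 × 0.12 = 0.143, printed as 0.14); IL-18 0.834/0.7 = 1.191; mtDNA 1.190; RIPK3 2.38/2.0 = 1.190; Table 8 rows 1.190 to 1.192.

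**Formula.** Two-sample t-test with df = n1 + n2 − 2 and noncentrality d × √(n1·n2/(n1+n2)); solve for the d that gives 80% power.

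| n (CO/placebo) | √(n1·n2/(n1+n2)) | d at 80% power | Power at d = 1.19 |
|---|---|---|---|
| 24/12 | 2.828 | 1.020 | 0.905 |
| 22/11 | 2.708 | 1.068 | 0.877 |
| 18/9 | 2.449 | 1.190 | 0.800 |

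The printed differences exceed the 24/12 values by 1.19/1.020 = 1.17, or 17%.

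**Can anything else give 1.19?**
- One-sided testing at 24/12 gives 0.90, further away.
- Mann-Whitney at its worst-case efficiency of 0.864 gives 1.0196/√0.864 = 1.097 (24/12) and 1.0680/√0.864 = 1.149 (22/11).
- Alpha of about 0.017 (24/12) or 0.025 (22/11) would give it, but the plan prints 0.05.
- 18 vs 9 reproduces 11 of the 15 values to the printed digit and the other four to within 0.2%. That is 25% loss from 24/12, which the plan states nowhere; that it was the basis is only an inference.

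**Differences at 80% power.**

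| Endpoint | SD | Printed | 24/12 | 22/11 |
|---|---|---|---|---|
| LIS | 0.8 | 0.95 | 0.82 | 0.85 |
| PaO2/FiO2 | 66 | 78.6 | 67.3 | 70.5 |
| OI | 10.1 | 12.0 | 10.3 | 10.8 |
| Vd/Vt | 0.12 | 0.14 | 0.122 | 0.128 |
| IL-18 (log) | 0.7 | 0.834 | 0.714 | 0.748 |
| mtDNA (log) | 1.0 | 1.190 | 1.02 | 1.07 |
| RIPK3 (log) | 2.0 | 2.38 | 2.04 | 2.14 |
| LTB4 | 17.95 | 21.4 | 18.3 | 19.2 |
| PGD2 | 0.68 | 0.81 | 0.69 | 0.73 |
| PGE2 | 1.68 | 2.00 | 1.71 | 1.79 |
| PGF2α | 1.15 | 1.37 | 1.17 | 1.23 |
| TXB2 | 12.38 | 14.75 | 12.6 | 13.2 |
| RvD2 | 12.18 | 14.5 | 12.4 | 13.0 |
| Mar1 | 15.29 | 18.2 | 15.6 | 16.3 |
| RvE1 | 10.54 | 12.55 | 10.7 | 11.3 |

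**RIPK3 fold.** The log must be natural: exp(0.834) = 2.3 and exp(1.190) = 3.3 match the text's 2-fold and 3-fold, whereas base 2 gives 2.3-fold for mtDNA and base 10 gives 6.8-fold for IL-18. Then exp(2.38) = 10.8-fold. At 80% power the detectable fold is 7.7 at 24/12 and 8.5 at 22/11.

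**Power for the text's own benchmarks**, read as differences in log means:

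| Benchmark | d | 24/12 | 22/11 | 18/9 |
|---|---|---|---|---|
| IL-18, 3-fold | ln 3/0.7 = 1.57 | 99% | 98% | 96% |
| mtDNA, 4-fold | ln 4/1.0 = 1.39 | 97% | 95% | 90% |
| RIPK3, 7-fold | ln 7/2.0 = 0.973 | 76% | 72% | 63% |

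**Table 6.** All 14 cells equal 1 − (1 − p)^22 or 1 − (1 − p)^11 to two decimals. At p = 0.10 the table prints 0.90 and 0.69; 22 and 11 give 0.90 and 0.69, while 24 and 12 give 0.92 and 0.72. The largest gap is about 3 points.

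**The case against.** The strongest reply is that nothing depends on these tables. The sample size of 36 rests on COHb precision, the endpoints are secondary or exploratory, section 9.4.3 itself warns that only large changes can be seen, and the error understates what the trial can do. That stands, and it limits the weight of the point.

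A second reply is that the printed values may be the more realistic ones. Days 4 to 7 are assessed only in subjects still hospitalized, some data collection stops after 48 hours of unassisted breathing, and mortality is high, so fewer than 24 and 12 may be evaluable. This is plausible, but the text attributes the figures to 24 and 12. It is a reason to state an evaluable number, not to leave it unstated.

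Third, the planned analyses are repeated-measures ANCOVA for Table 7 and principal components for the lipid mediators, so any t-test figure is nominal. That is true of the printed and the recomputed values alike. Baseline adjustment would normally lower the detectable difference, so it does not explain 1.19.

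On RIPK3, feasible need not mean 80% power, 76% is not far short, and the 7-fold figure is a ratio of medians between different patient groups. The wording can therefore be qualified rather than removed. But the paragraph sets the benchmark against 80%-power differences, and 7-fold falls below the detectable fold as printed, as exponentiated and as recomputed.

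**Conclusion.** The point holds. The printed differences correspond to about 90% power at 24 vs 12 and 88% at 22 vs 11, not 80%, and are about 17% larger than the stated 24 vs 12 supports. This rests on a two-sided, equal-variance t-test; no other stated input closes the gap. The RIPK3 fold is misstated (10.8, not 8-10), and feasibility at 80% power is not shown for RIPK3 at any of the sample sizes considered. It is shown for IL-18 and mtDNA. Table 6 is a labelling mismatch of at most about 3 points, in the conservative direction. None of this alters the sample size, the design or the primary analysis, but the stated power figures are wrong as written and should be corrected.

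**What to change.** - **Tables 7 and 8 and the log-biomarker text:** replace the differences with the 24/12 or 22/11 values above and name the numbers used. Alternatively, keep the printed values and state the evaluable numbers and attrition that produce them. Attributing them to a different alpha would contradict the printed 0.05.
- **RIPK3:** give the fold as 7.7 (24/12), 8.5 (22/11) or 10.8 (if 2.38 log is kept). Take RIPK3 out of the feasibility sentence, or add that a 7-fold difference has 76% power at 24/12.
- **Table 6 and its text:** relabel the columns as 22 and 11 evaluable, or give values for all dosed subjects, which fits section 9.3. For n = 24 these are 0.21, 0.38, 0.57, 0.71, 0.92, 0.98, 0.995; for n = 12 they are 0.11, 0.22, 0.35, 0.46, 0.72, 0.86, 0.93.
- **Section 9.2, wording only:** the >99% claim is correct for a half-width of at most 0.5%. The range −0.353% to 0.647% is 0.1467 ± 0.5, so call it the tolerance; the expected half-width is about 0.25% to 0.27%.

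The cost is text and table cells, with no change to enrolment, design or analysis. If the values are recomputed, every detectable difference gets smaller; RIPK3 comes closer to 7-fold but still does not reach it at 80% power.

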9 STATISTICAL CONSIDERATIONS

9.1 STATISTICAL HYPOTHESES

Hypothesis: We hypothesize that low dose iCO will be safe and well-tolerated and that the CFK equation-based iCO personalized dosing algorithm will be accurate in achieving a target COHb level of 6-8% in patients pneumonia (without ARDS and sepsis or with sepsis without ARDS criteria) and with sepsis-induced ARDS at study entry.

We further hypothesize that precision-based iCO therapy will reduce the severity of pneumonia and ARDS and organ failure by suppressing mitochondrial dysfunction, inhibiting inflammasome activation and necroptosis, and accelerating resolution of inflammation.

Primary Endpoints:

1. The primary endpoint is **safety of iCO**, defined by the incidence of pre-specified administration-related AEs and SAEs.

Administration-related SAEs are: 1) myocardial infarction; 2) stroke; 3) new onset arrhythmia requiring DC cardioversion; 4) worsening hypoxemia^{1,2}; 5) COHb \geq 10%; and 6) increase in lactate by \geq 2 mmol/L.

2. **Accuracy** of the CFK equation-based personalized iCO dosing algorithm to achieve a COHb level of 6-8%.

Secondary Endpoints:

1. Lung Injury Score (LIS) on days 1-5 and day 7
2. PaO₂/FiO₂ ratio on days 1-5 and day 7
3. Oxygenation index (OI) on days 1-5, and 7
4. Dead space fraction (Vd/Vt) on days 1-3 and day 7
5. Sequential Organ Failure Assessment (SOFA) scores on days 1-5, 7, 14, and 28
6. Ventilator-free days at day 28
7. ICU-free days at day 28
8. Hospital-free days to day 60
9. Hospital mortality to days 28 and 60
10. Neurocognitive function at 3 and 6 months

Exploratory Endpoints:

1. Plasma and urine biomarkers of mitochondrial dysfunction (mtDNA)
2. Plasma and urine biomarkers of inflammasome activation (IL-18)
3. Plasma and urine biomarkers of necroptosis (RIPK3)
4. Plasma Lipid mediators (LM) and specialized pro-resolving mediators (SPMs)

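### Section 9.4.3 gives SOFA, scored on eight days, the ANCOVA meant for one-value endpoints and names no day, summary, time term or within-patient term

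*Combined protocol and SAP*

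**What the plan says.** Section 9.1 (and likewise the synopsis and section 3) lists the endpoint as "Sequential Organ Failure Assessment (SOFA) scores on days 1-5, 7, 14, and 28". That is eight scheduled post-baseline scores, and the Schedule of Activities adds one at baseline.

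Section 9.4.3 treats the repeated secondary endpoints in two ways. LIS, PaO2/FiO2, oxygenation index and dead space fraction get "repeated measures analysis of covariance (ANCOVA) to assess the effects of treatment, time, and the interaction between time and treatment", with baseline values and named covariates. SOFA appears later, alongside ventilator-free, ICU-free and hospital-free days: "Sequential Organ Failure Assessment (SOFA) scores will each be analyzed separately using ANCOVA with treatment arm as the main effect". The same section adds "Age and sex will be considered as important biological variables in all analyses", and says of power for this group only "Given our modest sample size, we will only be powered to see large changes".

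The general approach in 9.4.1 offers two-sample tests and does not fill the gap. Under section 8.6, assessments from Day 4 onward are made only while the patient is still in hospital. A footnote to the Schedule of Activities lets the last SOFA be taken on Day 28 or at discharge.

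**The concern.** The patient is the unit of randomisation, and each can contribute eight correlated SOFA scores. An ANCOVA described only by its treatment effect is complete for an endpoint with one value per patient, such as ventilator-free days. For SOFA it leaves open what the outcome variable is and how scores from one patient are linked. The plan writes repeated-measures wording where it intends it, including for 90-minute COHb over three days (9.4.2), so its absence here is a real difference in the text.

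SOFA is the only listed endpoint that scores organ failure, and 9.1 hypothesises that inhaled CO reduces organ failure. If the outcome is settled after the data are seen, a chance benefit or harm is easier to find than the nominal 5% implies. The late scores add a further difficulty: they come from patients still in hospital, so an analysis that ignores day can compare different mixes of days between arms.

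**Working it through.** The documents give no SD, correlation, power or error rate for SOFA, so there is no figure of the plan's to reproduce.

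**Inputs.** From the plan: 24 CO and 12 placebo patients, and eight post-baseline days. Alpha 0.05 is stated in 9.4.3 for LIS; it is assumed here for SOFA, two-sided. Also assumed: within-patient correlation ρ, equal between all pairs of scores, varied from 0.1 to 0.9.

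**Reading 1: all patient-days pooled as independent rows (up to 36 × 8 = 288).** The true variance of the arm difference exceeds the assumed one by the design effect 1 + 7r. Here r = ρ without baseline adjustment. With it, r = (ρ − ρ²)/(1 − ρ²) = ρ/(1 + ρ). The false-positive rate is about P(|Z| > 1.96/√(1 + 7r)).

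Example at ρ = 0.5 with baseline: r = 0.333, design effect 3.33, threshold 1.96/1.826 = 1.07, rate 28%.

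**Reading 2: one ANCOVA per day, any p < 0.05 counted.** Eight independent tests would give 1 − 0.95⁸ = 33.7%. Correlation lowers this.

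**Reading 3: one pre-named day, or one mean per patient.** Each patient appears once, so the test is valid as it stands.

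Simulation under no effect, complete follow-up, 40,000 replicates per setting for readings 1 and 2:

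| ρ | Pooled, baseline-adjusted | Pooled, unadjusted | Any of 8 days, adjusted | Any of 8 days, unadjusted |
|---|---|---|---|---|
| 0.1 | 12.5% | 13.0% | 33.2% | 33.2% |
| 0.3 | 23.0% | 26.9% | 31.5% | 30.1% |
| 0.5 | 28.7% | 36.0% | 29.5% | 25.3% |
| 0.7 | 32.7% | 42.8% | 27.6% | 19.3% |
| 0.9 | 35.6% | 48.4% | 26.2% | 12.3% |

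Reading 3 gave 4.2-5.6% in every scenario run.

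**Sensitivity, baseline-adjusted.**

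- Correlation decaying with time (0.8-0.95 per day): pooled 23-29%, any-day 24-28%.
- Assumed attrition to 35% still scored at Day 28: pooled 22-31%, any-day 25-32%.
- A shared fall in SOFA lowers the pooled rate, because variation between days that the model ignores inflates its residual. At ρ = 0.5 with an assumed SD of 3 points, a linear fall of 0, 3, 6 or 9 points gives about 28%, 25%, 18% and 11%. A fall of three SDs is an extreme case.

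**What a single day gives up.** Take an assumed constant effect of 0.8 SD with baseline adjustment. The standard error is s × √(1/24 + 1/12) = 0.354s. For one day s = √(1 − ρ²). For the mean of the five scores on Days 2, 3, 4, 5 and 7, s = √[(1 − ρ²)(1 + 4r)/5].

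- At ρ = 0.5, one day: s = 0.866, 0.8/(0.354 × 0.866) = 2.61, power about 72%.
- At ρ = 0.5, Day 2-7 mean: s = 0.592, 0.8/(0.354 × 0.592) = 3.82, power about 96%.

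These closed forms ignore chance baseline imbalance. Simulation over ρ = 0.3-0.7 gives about 62-86% for one day and 95-99% for the mean.

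**The case against.** A reader might infer that the plan will pool patient-days as independent rows or run eight unadjusted daily tests, and hence that however the sentence is run the error rate is inflated. The documents do not support that. Neither analysis is stated. Listing SOFA with single-value endpoints fits one value per patient at least as well, and that reading holds 5%. The sentence is also not a full model statement: it names no covariates although it says ANCOVA, and age and sex apply to all analyses. Silence on a day or patient term is not exclusion of it, least of all by a team that writes repeated-measures models elsewhere. This objection stands, and the defect is under-specification.

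Two further points stand. The any-day figure is a family-wise rate, and the plan claims no family-wise control over its ten secondary endpoints. The pooled figure depends on a correlation and a time trend that the documents do not give, so no narrow range can be defended.

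What the objection does not remove is that the safe reading needs a day or summary fixed in advance, and none is. Chosen after the data are seen, it brings back the problem of selecting among eight days. The text on missing data in 9.4.3 centres on long-term outcomes and does not say what happens to SOFA scores after death or discharge.

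**Conclusion.** The point holds as a gap in specification with a better method at hand. Section 9.4.3 assigns an eight-day endpoint the analysis of a one-value endpoint and does not say which value is meant.

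The size depends on the reading: roughly 12-48% false positives if rows are pooled (somewhat lower under a very steep shared decline); about 25-33% family-wise in most baseline-adjusted day-by-day scenarios; and 5% for one pre-named day or summary. Even against that valid single-day reading, using the repeated scores gains power, from about 62-86% to 95-99% for a constant 0.8 SD effect. Correlation, trend, attrition and effect size are assumptions throughout.

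The consequence is limited to interpreting one secondary endpoint; the primary endpoints, safety and dosing accuracy, are untouched. The change should be made, but the trial does not depend on it.

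**What to change.** In 9.4.3, take SOFA out of the free-days sentence and add it to the repeated-measures ANCOVA used for LIS: baseline SOFA, treatment, categorical day, treatment by day, the named covariates, and a patient random effect or another parsimonious covariance. An unstructured matrix over eight visits has 8 × 9/2 = 36 parameters, too many for 36 patients.

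Pre-name one between-arm contrast as the SOFA result, for example the mean difference over the early in-hospital days such as Days 2-7. Report individual days, including 14 and 28, as descriptive estimates with confidence intervals. State how scores missing through death or discharge are handled. Keep plain ANCOVA for the free-day endpoints.

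The mixed model itself has had only a light check: 3.5% false positives at ρ = 0.5 in 400 replicates, with some convergence warnings. A baseline-adjusted ANCOVA of each patient's mean over the named days is a simple fallback and held close to 5% in simulation.

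The cost is a few sentences and no new data. Single-day SOFA p-values would no longer be claimed as findings.
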